## **27.2 Sample size justification for primary aims and trial endpoint**

Our TOTAL sample size ensures adequate power to test all *three* primary aims. For the observational group, a sample size of 60 with complete follow-up matches our intervention arm and ensures an

adequate comparison group size to test unknown effects of AIs on BD as measured by fat/water-MRI as well as to assess the two additional endpoints of pain and hypertension.

To justify the sample size for the sulindac intervention, we considered the primary trial endpoint, which is to compare the difference in the slope of the FWR-MRI-derived log (Fra50) between the baseline and sulindac treatment periods. Based on previous findings using mammographic density measures in randomized trials of AI (see Table 1), we assume there will be no more than a 5% change during the 12 month on intervention study and only a 1-2 % difference between the two baseline periods (observational period in the intervention arm of 3 months) due to between measurement variability. For the sulindac treated group, we assume an initial sample size of 100 women and allow the possibility of up to 20% dropout for the end of intervention follow-up measurement. This results in at least 80 evaluable women.

With 80 women we will be able to detect a decrease of 0.368 standard deviation (SD) units in the slope while on sulindac treatment versus the baseline slope with 80% statistical power, assuming a two-sided  $\alpha$  of 0.017 (*adjusted for multiple comparisons*). To estimate what this change would be in relation to BD, we used the relationship between BD and log(Fra50) from our previous study. Based on an analysis of our cross-sectional data, the estimated SD of log(Fra50) is 2.40. Thus, a decrease of 0.368 SD units corresponds to a change of -0.883 (-0.368\*1.40). Based on the regression line, this is equivalent to a 4% average decrease in BD as determined by CAD assisted BD by mammography. Note, that while this is the effect size that we are able to detect, enthusiasm for the potential to move sulindac forward for an efficacy trial would be much greater with average decreases of more than double that of projected age related change. Thus, the study is well powered to detect even small differences. However, effect sizes < 8% average decrease in Fra50 will not be considered highly impactful in interpreting the results from a clinical perspective given the average age-related decline in BD is 1-3%.

To insure that the use of the new methodology of FWMRI yields a similar change in BD over 12 months and that we interpret change in the sulindac intervention in a more informed manner, a cohort of women similar to those in the sulindac intervention will be followed for BD using FWMRI at 0, 6 and 12 months. Assuming an 80% complete rate, we will have 60 women for complete analysis. To detect a decrease of 0.368 standard deviation (SD) units in the slope while on observation, assuming a two-sided  $\alpha$  of 0.05 (single test), we will have >80% to detect a 3% average decrease in BD at 12 months similar to that determined by standard mammography and CAD. This value will be considered when 'interpreting' the impact of any effect size observed in the sulindac arm. This will not however be used in a statistical analysis as a comparison group.

Justification of the sample size for the additional primary specific aims for the intervention with sulindac. For the BPI-SF past-week worst-pain score (Aim 2), we hypothesize that sulindac treatment will lead to a decrease in pain scores compared with baseline. The standardized decrease of 0.368 SD units corresponds to a 0.8-unit decrease, based on the SD of 2.25 observed at baseline in a recent study of acupuncture for AI-associated joint symptoms as referenced in the original grant submission. For Aim 3, we hypothesize no additional grade 2 or higher hypertensive adverse events in women taking sulindac compared to the same women during baseline. The power for McNemar's test depends heavily on the number of discordant pairs (i.e., those women who have grade 2 or higher hypertensive adverse events on either sulindac or baseline, but not both or either). We hypothesize that only 10% of the women will be discordant, since we expect almost 90% will not have grade 2 or higher hypertension during either period. The sample size of 75 women will allow us to detect an increase to 9% of women with grade 2 or higher hypertension when taking sulindac but not during the baseline period, versus 1% of women during the baseline period but not while taking sulindac, with 77% statistical power (assuming a one-sided test at  $\alpha = 0.05$ ).

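### Protocol 27.2 converts the detectable 0.368 SD in the sulindac arm to a 4% density decrease with a cross-sectional SD, not the SD of the within-woman slope difference under test, so the 4% does not follow

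*Protocol*

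**What the plan says.** **Sulindac arm, Protocol 27.2.** With 80 evaluable women, 80% power and a two-sided alpha of 0.017, the detectable effect is a decrease of 0.368 SD in the on-treatment slope relative to the baseline slope. It is then converted to density. The SD comes from a single-time-point analysis: "Based on an analysis of our cross-sectional data, the estimated SD of log(Fra50) is 2.40". From this, "a decrease of 0.368 SD units corresponds to a change of -0.883", with a bracket that shows the multiplier as 1.40. Using a regression line from an earlier study, "this is equivalent to a 4% average decrease in BD as determined by CAD assisted BD by mammography". The paragraph concludes that "the study is well powered to detect even small differences", and adds that "effect sizes < 8% average decrease in Fra50 will not be considered highly impactful".

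**The test, Protocol 27.1.** Each woman contributes a no-drug slope from the scans at 0 and 3 months and an on-drug slope fitted to the scans at 3, 9 and 15 months. The mean slopes are compared with a paired t test.

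**Observation arm, Protocol 27.2.** With 60 completers and a two-sided alpha of 0.05, the text begins "To detect a decrease of 0.368 standard deviation (SD) units in the slope while on observation" and ends "we will have >80% to detect a 3% average decrease in BD at 12 months similar to that determined by standard mammography and CAD". No SD or conversion is shown. Section 27.1 says the analysis is a within-woman slope over 0, 6 and 12 months.

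**Variability figures elsewhere.** Section 6.1 puts FWMRI between-measure variability at 1-2%, and 27.2 assumes "only a 1-2 % difference between the two baseline periods". Sections 4.2 and 6.1 cite a mean mammographic change of -1.3% (±2.9%) at two years in healthy postmenopausal women. Section 27.2 uses none of these as an SD.

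**The concern.** A standardised effect becomes a density change only when it is multiplied by the SD of the quantity being tested. Here that quantity is, for each woman, her on-drug slope minus her no-drug slope. Its SD depends on scan error, on the spacing of the scans and on how much true slopes differ between women. The spread of log(Fra50) between women at one time is a different quantity. It contains stable differences between women that cancel out of a slope, and it takes no account of the short three-month baseline interval, which magnifies scan error in the annualised no-drug slope.

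The 4% is the only density figure offered for the sensitivity of the primary endpoint, and it carries the statement that the study can detect small differences. A reader of the results who takes it as the design's established sensitivity relies on a number with no basis. The true detectable change could be smaller or larger.

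**Working it through.** **1. Reproduce the SD-unit power.** One-sample (paired) t test, noncentral t, df = n - 1, noncentrality = 0.368 × √n.
- Sulindac: n = 80, two-sided 0.017: power 80.1%.
- Observation: n = 60, two-sided 0.05: power 80.1%.

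Both standardised statements are right. That 0.368 appears in both arms is a coincidence of n and alpha.

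**2. Reproduce the conversion.**
- 0.368 × 2.40 = 0.883, the printed result.
- 0.368 × 1.40 = 0.515, which is what the printed bracket would give. The 1.40 is evidently a misprint.

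**3. What SD does the test need?** Measure time in years and give each scan an independent error with SD σ.
- On-drug slope (3, 9, 15 months): scan at 15 minus scan at 3, since the middle scan has zero weight.
- No-drug slope: 4 × (scan at 3 minus scan at 0).
- The difference has weights 4, -5, 0, 1 on the scans at 0, 3, 9 and 15 months. Variance = (16 + 25 + 0 + 1)σ² = 42σ².

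**4. How far can 4% move?** Assume that 2.40 is the total SD of one log(Fra50) measurement, that visit-to-visit correlation is ρ (so σ² = (1 - ρ) × 2.40²), that true slopes do not vary, and that the protocol's ratio of 4% BD to 0.883 log units is proportional. The slope-difference SD is then 2.40 × √(42(1 - ρ)).

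| Assumed ρ | SD of slope difference | 0.368 SD, log units | BD equivalent |
|---|---|---|---|
| 0.50 | 11.0 | 4.05 | 18% |
| 0.80 | 6.96 | 2.56 | 11.6% |
| 0.90 | 4.92 | 1.81 | 8.2% |
| 0.95 | 3.48 | 1.28 | 5.8% |
| 0.98 | 2.20 | 0.81 | 3.7% |
| 0.99 | 1.56 | 0.57 | 2.6% |

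The slope-difference SD equals 2.40 only where 42(1 - ρ) = 1, that is ρ = 41/42 = 0.976. Variation in true slopes would raise every row. The documents do not give ρ.

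**5. Cross-check from the 1-2% figure.** Read it in BD points and as scan error only (both assumptions).
- As a single-scan SD: √42 × 1 to 2 = 6.48 to 12.96 points per year. Detectable effect 2.4 to 4.8 points.
- As the SD of a between-scan difference (σ = 0.71 to 1.41): 4.58 to 9.17 points per year. Detectable effect 1.7 to 3.4 points.

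The 4% lies within the first range and above the second.

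**6. Observation arm.** The smallest effect with 80% power for n = 60 at two-sided 0.05 is 0.3677 SD. Power for 3 points is therefore at least 80% when the 12-month slope SD is at most 3 / 0.3677 = 8.16 points.
- If ±2.9% is an SD (assumption; mammography, two years, healthy women): power above 99.9%.
- With that SD doubled to 5.8: power 97.6%.
- Scan error alone at the largest reading: slope SD √2 × 2 = 2.83 points, well below 8.16.

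**The case against.** The strongest defence is that the consequence is small. Protocol 4.4 says accrual and participation are concluded. The SAP makes the analysis after 40 sulindac completers the primary one, fits a mixed model to log-transformed BD, plans no test between groups and reports BD change with 95% confidence intervals. Those intervals, not the 4%, will show what the trial could resolve. This stands and is why the point is minor. It does not rescue the 4%, which remains in the current protocol with no replacement calculation in the SAP.

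A second defence is that the density conversion rests on a regression line from an earlier study that is not in the documents. That is true, but the difficulty comes one step before: the SD put into that line is of the wrong kind, whatever its slope.

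A reader might infer three stronger things that the documents do not support.
- *The observation arm's power claim is false.* It is an inequality, true for any slope SD up to about 8.16 points, and the variability figures the documents do give are consistent with it. Only the derivation is missing.
- *0.368 SD cannot be 4% in one arm and 3% in the other.* The protocol never equates 0.368 SD with 3%. A single slope and a slope difference also have different SDs, so the two figures do not contradict each other.
- *The sample size is wrong or the trial underpowered.* The standardised power reproduces, and the true detectable change may be below 4%.

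Nor is it clear that a power figure will be used to judge the sulindac effect. Sections 4.2 and 6.1 indicate that the change actually observed in the observation group will inform interpretation.

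**Conclusion.** The point holds for the sulindac arm's conversion and is minor. The 4% BD equivalent comes from a cross-sectional SD where the SD of a within-woman slope difference is required, and neither document supplies the latter. The claim of good power for small differences, drawn from it, is therefore unsupported. It is not shown to be false.

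The size of the error cannot be fixed from the documents. The range of about 18% to 2.6% BD rests on assumed correlations of 0.5 to 0.99, independent scan errors, no true slope variation and a proportional conversion. It shows how sensitive the figure is and does not estimate the trial's power.

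The observation arm's claim for 3% is underived but conditionally sound. Two smaller defects in the sulindac paragraph are certain: the 1.40 misprint, and an impact threshold stated on Fra50 beside a detectable effect stated on BD.

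**What to change.** In the sulindac paragraph of Protocol 27.2:
- Withdraw the 4% equivalent and the sentence claiming good power for small differences. State only that, with 80 women, the paired t test has 80% power at two-sided 0.017 for 0.368 SD of the within-woman slope difference. Note beside it that the SAP's primary analysis is now a mixed model after 40 completers.
- If a BD equivalent is wanted, give 0.368 times the SD of the within-woman slope difference from the study's own scans at 0, 3, 9 and 15 months, labelled retrospective. Repeat-scan data alone would supply only the scan-error part.
- If the conversion line stays for the record, correct 1.40 to 2.40 and say that it uses a cross-sectional SD.
- Put the 8% threshold and the detectable effect on one named scale, BD or Fra50.

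In the observation-arm paragraph, keep the claim of more than 80% power for 3% only with its condition: a 12-month slope SD of at most about 8.16 BD points.

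The cost is a wording change. The optional BD figure needs one SD from scans already collected. No new data are needed and the planned analysis does not change.

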### **27.3 Conduct of and Justification for Planned Futility Analysis**

As discussed in the funded grant submission, we would like to limit women's exposure to agents that are unlikely to effect change in the breast in a clinically meaningful way. Therefore, we will include a futility analysis for the primary trial endpoint of FWR log(Fra50) after 40 women have reached the 15-month endpoint. This analysis is for futility only, so it will not affect the overall  $\alpha$  level. Briefly, the observed results from these women will be used to compute the difference between the slope during sulindac treatment versus the baseline period. Predicted results for future participants will be generated from a log-normal distribution with the observed mean and SD. One thousand bootstrap samples with a sample size of 80 women will be generated to estimate conditional power. The study will continue if conditional power  $\geq 80\%$  is met. If we fail to pass futility, we plan to **stop accrual to the study and suspend study agent for women who are active**. We plan to follow all women who initiated trial agent to their next imaging endpoint (9 or 15 months, whichever comes first). Considering a dropout rate of 10% by 9 months and 20% by 15 months, and a planned accrual rate of 5 participants/month starting in month 6 of funding, we expect to have 40 evaluable participants followed to 15 months by approximately 3 years; by then, ~90 participants will have completed 9-month measures, and ~100 will have initiated the trial.

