### **30.3 Plan for assuring data accuracy and protocol compliance**

Routine study activity and safety information will be reported to the DSMB every six months, or more frequently if requested. These reports will include:

- a. Study activity, cumulative and for the period under review;
- b. Safety (narrative description on non-serious and serious adverse events);
- c. Predetermined protocol early stopping rules for efficacy/futility;
- d. Monitoring and protocol compliance;
- e. Comments
- f. Annual reports from specialty DSMB for review of cardiovascular toxicity
- g. Attachments (AE data reviewed by the PI to compile the report, SAE letters and reports, results of any review(s), applicable correspondence with the IRB or other regulatory agencies.
- h. Data, safety and study progress will be reported to:
  - I. Human Subjects Protection Program (IRB) at least annually;
  - II. Sponsor (if applicable) at least every six months.
  - III. Sponsor or funding agency, as applicable: The PI will immediately notify, in writing, the funding agency, if applicable, any action resulting in a temporary or permanent suspension of the study.

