In consultation with NCI, concern was raised that prior studies of AIs showing no effects of AIs on BD were based on mammography and not the more sensitive MRI method under investigation. As such, an observational (non-randomized) control group comprised of BC patients stable on an AI was included specifically to monitor for AI effect on BD using the MRD method.

Initially, the target sample size was reduced to 75 and 60 in the intervention and observation groups, respectively. A previously planned futility analysis of SUL effect on MRD after 40 participants completed 12 months of intervention was changed to the primary analysis on limited resources and slow accrual. Patients consented to banking tissue biopsies for future biomarker studies.

Modified Study Hypotheses: Because of the modification to the study design, the study hypotheses were modified as follows:

Primary

SUL 150 mg BID for 12 months will decrease MRD in postmenopausal women taking aromatase inhibitor therapy.

- a. As a sensitivity analysis of this primary hypothesis, per-study analysis described below will also be performed using only subjects who are adherent with study protocols (adherence is defined as having taken at least 80% of study agent).
- b. As a sensitivity analysis of this primary hypothesis, per-study analysis for primary hypothesis will also be performed using only those subjects with baseline BD $\geq 15\%$.

Secondary

SUL 150 mg BID for 12 months will be well tolerated and grade 3 adverse events will not exceed 10% and patients who drop out secondary to adverse events will not exceed 10%. *With low sample size of 40, only when there are no grade 3 AE or drop out secondary to AEs, can say it will not exceed 10% (point estimate is 0% with 95% Blyth-Casella-Still CI (0-7.78%).*

Reportable Outcomes

1. Change in BD from baseline at 6 and 12 months by MRD in postmenopausal women receiving AI for treatment of breast cancer and 95% confidence interval will be reported separately for:
 - a. participants in the sulindac group who started sulindac and who had at least one MRD measure on intervention,
 - b. participants enrolled and started in the observation arm with at least one MRD measure post baseline,
 - c. participants adherent to SUL intervention (same caveats as a), and

- d. in both arms but reported separately for participants with baseline BD $\geq 15\%$ (same respective caveats as a and b).

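### The 80% power in Protocol 27.2 makes no allowance for the 27.3 futility rule, and no power is given for the 40-completer analysis that the SAP put in its place

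*Protocol*

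**What the plan says.** Protocol 27.2 bases the sulindac arm on the primary endpoint, the within-woman difference in log(Fra50) slope between the treatment and baseline periods: "With 80 women we will be able to detect a decrease of 0.368 standard deviation (SD) units" in that slope "with 80% statistical power, assuming a two-sided" alpha of 0.017, which is 0.05 shared among three endpoints.

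Protocol 27.3 plans a futility look once 40 women reach 15 months. "Predicted results for future participants will be generated from a log-normal distribution with the observed mean and SD", and 1,000 samples of 80 women are drawn to estimate conditional power. "The study will continue if conditional power" is at least 80%. Otherwise accrual stops and agent is suspended for active women. The section notes that alpha is unaffected and does not mention power.

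The SAP (last modified November 2019), in its account of the study modifications, reports: "A previously planned futility analysis of SUL effect on MRD after 40 participants completed 12 months of intervention was changed to the primary analysis", because of limited resources and slow accrual. Protocol 4.4 says accrual and participation are concluded. Protocol 30.3 still lists, among the contents of reports to the DSMB, "Predetermined protocol early stopping rules for efficacy/futility".

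**The concern.** A futility look costs no alpha but does cost power, because some trials that would have succeeded are stopped. The loss is small when the continuation threshold is low. Here the threshold equals the design power and the projection uses the interim estimate rather than the design effect. A trial running exactly as planned therefore sits close to the boundary, and 27.2 gives its power as though no boundary existed.

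The second issue is which plan applies. The protocol describes a gate at 40 and a final test at 80. The SAP describes a final analysis at 40. A reader who takes power from 27.2 and the analysis from the SAP will credit a 40-woman analysis with the power of an 80-woman test.

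**Working it through.** **Inputs.** Effect d = 0.368 SD, final n = 80 and two-sided alpha 0.017 (27.2); paired t test of slopes (27.1); look at n = 40, projection from the observed mean and SD, threshold 80% (27.3).

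**1. Stated power.** For a paired t test, power = 1 − F(c; 79 df, noncentrality d√n). Here c = 2.438 and d√n = 0.368 × 8.944 = 3.291, so power is 80.1%. The 80% figure reproduces, with no futility look.

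**2. What 27.3 requires at the look.** Write e for the observed effect at 40 women in SD units. The text allows two readings.
- A: keep the 40 observed women and predict 40 more. Conditional power ≈ Φ[(√80·e − c)/√0.5]. Setting this to 0.80 gives e = (2.438 + 0.842 × 0.707)/8.944 = 0.339.
- B: draw all 80 afresh from the observed mean and SD. Conditional power is the step 1 formula with e in place of d, so e must be about 0.368, the design effect itself.

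**3. Effect on power.** I simulated 200,000 trials at each true effect, with normal slope differences, the look at 40 and the final t test at 80.

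| True effect | Stopped, A / B | Power with rule, A / B | Power without rule |
|---|---|---|---|
| 0.368 SD | 42.3% / 49.1% | 54.7% / 48.7% | 80% |
| 0.5 SD | 16% / 21% | 84% / 79% | 98% |
| 0.736 SD (twice design) | 0.7% / 1.2% | 99.3% / 98.8% | >99.9% |

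Explicit resampling with 1,000 draws per look (6,000 trials at 0.368 SD) gives 42.4% / 49.2% stopped and 54.7% / 48.9% power.

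The closed form with known SD uses the normal critical value 2.387. The continuation limits become 0.333 and 0.361, and the stopping probabilities Φ[(0.333 − 0.368)√40] = 41% and Φ[(0.361 − 0.368)√40] = 48%. Power from the bivariate normal (correlation √0.5) is 56% and 50%.

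**4. The log-normal.** The figures above assume normal slope differences, which fits 27.3 if log-normal describes Fra50 and hence means normal on the analysed log scale. Applied literally to the slope difference it cannot be used, because a log-normal takes only positive values and a decrease is expected. With the sign flipped and the mean and SD matched (3,000 trials, stopping when the observed mean has the wrong sign), the rule stops about 22% (A) or 8% (B) at 0.368 SD and leaves 70% or 79% power. The wording therefore changes how the rule behaves.

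**5. The 40-completer analysis.** With n = 40, d√n = 0.368 × 6.325 = 2.327. The step 1 formula with 39 df gives 44% power at alpha 0.017 (c = 2.493) and 62% at 0.05 (c = 2.023). The 95% half-width is 2.023/√40 = 0.32 SD. These are illustrations, since the SAP uses a covariate-adjusted mixed model.

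**The case against.** The strongest reply is that the rule is obsolete. The SAP replaced the look, and Protocol 4.4 says accrual and participation are over, so there is nobody left to stop enrolling or to take off agent. This stands. A reader might infer that the trial really had about 50% power because of a futility stop, but the documents do not show that the gate was ever applied.

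The protocol carries January 2021 content, later than the SAP, which could suggest that the rule was reaffirmed and is still held by the DSMB. That content concerns laboratory relocation and sample transfer. The line in 30.3 is a general list of report contents that also names efficacy stopping, for which the protocol has no rule. Neither shows that 27.3 remains in force.

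The log-normal might be thought to cause the 42-49% stopping. It does not: that follows from the 80% threshold under normal draws, and a literal log-normal stops fewer trials.

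A strict gate can also be defended on the protocol's own aims. Section 27.2 equates 0.368 SD with a 4% density decrease and regards effects below 8% as not highly impactful, and at twice the design effect the rule does almost no harm. That justifies choosing a demanding rule. It does not justify leaving its cost out of the power statement.

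Finally, one might say the look came too late to matter. At 5 women per month from month 6, the 100th enters near month 26 (6 + 100/5). Forty evaluable women need about 50 enrolled (20% loss), reached near month 16, so the look falls at about month 31; 27.3 itself says "we expect to have 40 evaluable participants followed to 15 months by approximately 3 years". Stopping accrual would then save little, but suspending agent would still limit exposure, so the rule was not empty.

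**Conclusion.** The point holds in limited form. The 80% in 27.2 is correct for a single test at 80 women and wrong for the design that 27.2 and 27.3 describe together, where power at the design effect is about 49-55%. That range assumes normal slope differences on the log scale, a true effect of 0.368 SD and either reading of the 80-woman projection. The loss is concentrated near the minimum detectable effect and almost vanishes at twice that effect.

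It is a statement about the protocol as written, not about the trial as analysed. What remains live is the mismatch: the protocol keeps a futility gate and an 80-woman power figure, the SAP makes the 40-completer analysis primary, and neither states what that analysis can detect or how precisely it estimates the change. This should be corrected, because the power credited to the primary result depends on it.

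**What to change.** - Mark 27.3 as withdrawn, refer to the SAP's change, and state whether the look at 40 was ever run as a futility gate before it became the primary analysis.
- In 27.2, replace the 80% figure with the power, or preferably the expected confidence-interval width, of the 40-completer analysis under the SAP's mixed model, and name the alpha used. The paired-test figures above show the likely order of size.
- If 27.3 is to stay on record as operative, restate the 27.2 power with the rule in place. Say whether the 40 observed women are kept in the projection, and specify normal draws on the log scale or resampling of the observed slope differences.

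The cost is protocol wording and one short calculation. The downside is that the stated power becomes less favourable.
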